2. Rate and percent of skin graft necrosis
 - a. We expect about a 20% rate of skin graft necrosis in the STSG group and about a less than 5% rate of skin graft necrosis in the Integra group. To test for a significant difference in the STSG and STSG with Integra groups, we will employ a chi-squared test of equal proportions. We will have 62% power to detect the difference between the two groups.

The Use of Integra[®] in Coverage of Radial Forearm Free Flap Donor Site Defect

Comprehensive Cancer Center of Wake Forest University (CCCFWU)

CCCFWU # 99915A

- b. In the STSG group, we expect about 10% of the graft to become necrotic, while we believe that below 5% of the STSG with Integra group to become necrotic. We will have approximately 16% power to detect this difference using a chi-squared test.
 - c. While the study may be underpowered to make this particular observation statistically significant, this parameter is not a primary objective of the study but will be easy to measure.
 3. Presence of pain and paresthesia and severity on a 1-10 scale
 - a. In the split thickness skin graft group, we expect about 20% of the subjects to still have pain at the radial forearm site, while about 35% of these subjects will have significant paresthesias. In the Integra group, we expect about 10% of the subjects to have pain at the radial forearm site, while about 20% of these subjects will likely have paresthesias. To test for significant difference in the two groups, we will again employ a chi-squared test. We will have 29% power to detect a significant difference in pain at the radial forearm site and 39% power to detect a significant difference in the rates of paresthesias.
 - b. Of the subjects that have pain we expect those who have had Integra[®] placed to have pain at a level of an average of about 3, while those who have not had Integra[®] will have pain at an average level of 7. After evaluating the distribution of the scaled scores, we will test if these means are equal using a t-test if data appear normal and a Wilcoxon Rank sum test if not. Assuming the two groups share a common standard deviation of 3, we will have over 99% power to detect this difference using a t-test. If data appears non-normal, assuming the probability that an observation in the Integra[®] group has lower severity of pain is 0.75, we will have 99% power to detect this difference.
 4. Aesthetic outcome of donor site on Vancouver Scar Scale

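### Item 3b tests pain severity only among subjects who have pain, a subset that treatment is expected to change, and its stated 99% power assumes that all 50 per arm have a score

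*Combined protocol and SAP*

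**What the plan says.** All of this is in section 13.0, Statistical Analysis, item 3, headed "Presence of pain and paresthesia and severity on a 1-10 scale". The item states no score for a subject without pain.

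- **Item 3a, presence.** Pain is expected in about 20% of the STSG group. For the other arm the plan says "In the Integra group, we expect about 10% of the subjects to have pain at the radial forearm site". The arms are compared by chi-squared, with a stated power of 29% for pain.
- **Item 3b, severity.** The sentence opens "Of the subjects that have pain we expect those who have had Integra[®] placed to have pain" and gives an expected mean of about 3 with Integra; "those who have not had Integra[®] will have pain at an average level of 7". It continues: "we will test if these means are equal using a t-test if data appear normal and a Wilcoxon Rank sum test if not".
- **Power for severity.** For the t-test: "Assuming the two groups share a common standard deviation of 3, we will have over 99% power to detect this difference using a t-test". For the Wilcoxon test: "assuming the probability that an observation in the Integra[®] group has lower severity of pain is 0.75, we will have 99% power".

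The same section plans 50 subjects per group and two-sided testing at 0.05. Section 5.0 has presence of pain surveyed at 3, 6 and 12 months.

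**The concern.** The means to be tested in item 3b are the ones just given, and those are means among subjects with pain. Having pain at follow-up is an outcome, and item 3a expects treatment to halve its frequency. The two sets of painful subjects are therefore not the randomised groups. A difference between them mixes the effect of treatment on severity with its effect on who is left to be scored. A larger trial would not remove this.

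At stake is a planned hypothesis test that could point the wrong way. If Integra mainly prevented mild pain, the remaining cases would be the severe ones and their mean would rise, although nobody was worse off and total pain fell.

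The power statement raises a second question about the same sentence. Only about 15 of 100 subjects are expected to enter the comparison, yet the stated power is 99% or more.

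**Working it through.** **Inputs from section 13.0:** 50 per arm; pain 20% v 10%; mean severity 7 (STSG) v 3 (Integra) among those with pain; SD 3; P = 0.75 for the Wilcoxon test; two-sided 0.05. The section states no dropout allowance, and none is used here.

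**1. Size of the subset.** 0.20 × 50 = 10 STSG and 0.10 × 50 = 5 Integra.

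**2. The plan's severity power, reproduced at 50 v 50.**
- t-test: noncentrality = 4 / (3·√(1/50 + 1/50)) = 4/0.6 = 6.67 on 98 df. Power is above 99.9%; the plan says over 99%.
- Wilcoxon (Noether): power = Φ(√(12·c(1−c)·N)·|P − 0.5| − 1.96), where c is the share of subjects in one arm. With c = 0.5 and N = 100: √300 = 17.32; 17.32 × 0.25 = 4.33; Φ(2.37) = 99.1%. The plan says 99%.

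Both figures match only if every subject has a severity score.

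**3. The same formulas at 10 v 5.**
- t-test: noncentrality = 4 / (3·√(1/10 + 1/5)) = 4/1.643 = 2.43 on 13 df. Power is 61.5% by the noncentral t (68.2% by normal approximation). Averaged over binomial variation in the two subset sizes it is about 57%.
- Wilcoxon: c = 2/3, N = 15: √40 = 6.325; 6.325 × 0.25 = 1.581; Φ(−0.379) = 35%. Simulation with the exact test gives about 30%.

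**4. Presence of pain (item 3a).** Pooled proportion 0.15: Φ[(0.10 − 1.96·√(2·0.15·0.85/50)) / √((0.16 + 0.09)/50)] = Φ(−0.565) = 28.6%, against 29% stated.

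**5. Can the direction reverse?** Assume ten STSG scores from Normal(7, 3), rounded and held within 1–10. Assume that Integra abolishes pain in the five mildest and changes nobody else. Over 200,000 simulated sets:
- Among those with pain: STSG 6.78, Integra 8.72. Integra looks 8.72 − 6.78 = 1.94 points worse.
- Over all 50, with 0 for no pain: STSG 10 × 6.78/50 = 1.36; Integra 5 × 8.72/50 = 0.87. Integra looks better.

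A check by hand, with five scores of 5 and five of 9: the subset means are 7 v 9, and the all-subject means are 70/50 = 1.4 v 45/50 = 0.9. The pattern is the same.

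**6. Power if everyone is scored.** Under the plan's rates, means and SD, expected means are 0.20 × 7 = 1.4 and 0.10 × 3 = 0.3 before rounding and clipping. Simulated power with scores rounded and clipped to 1–10 among those with pain is about 34% (Wilcoxon) and 62% (t-test).

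**7. Comparing steps 3 and 6.** The Wilcoxon figures, 35% and 34%, rest on different effects. Means of 7 v 3 with SD 3 imply P = Φ(4/(3·√2)) = 0.827. At 10 v 5 that gives 6.325 × 0.327 − 1.96 = 0.11, or about 54%. The subset test therefore has 35% at the plan's own P of 0.75, and about 54% at the effect used in step 6.

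**The case against.** Four points deserve weight.

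*The plan does not ignore pain-free subjects.* Item 3a compares presence of pain by chi-squared. In the extreme case above, the report would show 5/50 v 10/50 with pain beside the severity means, and a careful reader would see the benefit. This stands as partial mitigation. At 29% power the presence test cannot be relied on to correct a misleading severity result.

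*The illustration is one chosen pattern.* It keeps the plan's STSG figures but sets aside its expected Integra mean of 3. If instead every score falls by 1 to 5 points, and those dropping below 1 become pain-free, the subset means are 6.0, 5.2, 4.4, 3.8 and 3.2 against 6.8, all in the right direction. Even in the extreme case, a significant wrong-direction t-test occurs in about 28% of simulated trials. A reader might infer that the plan will make Integra look worse, or that errors in either direction are equally likely. The documents support neither; they show only that the comparison is unprotected.

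*The population may have been meant to be everyone.* The power figures fit 50 v 50, so a reader might take them as evidence of an all-subject analysis. The wording of item 3b is against that, and item 3 would then give pain-free subjects no score. Either reading needs repair.

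*The missing zero is not itself an error.* A reader might infer that a 1–10 scale is faulty. Within a pain-only subset it is not. The form and its anchors are not in the documents, and presence is recorded separately. Nor does item 3b plan a test of paresthesia severity, so the point does not extend to it.

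Pain severity is also absent from the numbered endpoint list in section 13.0, where the third entry is the rate of paresthesia. This limits the weight of the point but does not remove a planned test.

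**Conclusion.** The point holds as a possible bias, not a certain one. Item 3b tests means in a subset formed after randomisation that the plan expects treatment to change, about 10 v 5 subjects. If Integra mainly prevents mild pain, the result can reverse: 8.7 v 6.8 in the subset against 0.87 v 1.36 over all subjects. Those figures rest on the assumed score distribution and on Integra affecting only the five mildest cases.

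Separately, and without that assumption, the stated severity powers do not belong to the comparison described. They need 50 scores per arm; at the expected subset sizes they are about 62% (t-test) and 35% (Wilcoxon at P = 0.75). The change is worth making, for an outcome that is not central to the trial's objective.

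**What to change.** In section 13.0, item 3b:

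- Score subjects recorded as having no pain as 0. A subject whose pain status was not recorded stays missing.
- Compare severity over all randomised subjects with the Wilcoxon rank-sum test already named, and report a difference in means with its confidence interval.
- Present severity among those with pain as description only, beside the number with pain in each arm.
- Replace the stated 99% power with the recalculated figure, about 34% by Wilcoxon, and state its assumptions: the plan's rates, means and SD, with scores rounded and clipped to 1–10.

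A printed 0 anchor on the form is optional, because presence of pain is already collected. The cost is a few sentences and no new data.

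The downside is many tied zeros and a much less favourable stated power. Most of that fall corrects a figure the subset test never had: 34% is close to its 35% at the plan's P of 0.75. At the larger effect implied by 7 v 3 with SD 3, the Wilcoxon test does lose power, from about 54% to 34%. That is the price of a comparison that randomisation protects.

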13.0 Statistical Considerations

Endpoints:

1. Rate of tendon exposure. Previously reported from 12-55%. [7, 16-19]
2. Rate and percent of skin graft necrosis. Rate previously reported to be from 7%-51%. [7, 9, 16, 20-22]
Percentage of skin graft loss ranges from $\leq 5\%$ - $\geq 20\%$. [9, 16]
3. Rate of paresthesia. Previously reported to be 36%- 50%. [9, 20]
4. Aesthetic outcome of donor site on Vancouver Scar Scale, a validated objective assessment of scar appearance. [23] Previous scores are reported to be 4.7/13 without Integra and 4.2/13 with Integra. [14, 24]
In particular, we will be focusing on the pliability aspect of the Vancouver Scar Scale, which will be a measure of the functionality of the skin overlying the donor site. The scores will be taken at the 3,6, and 12 month follow up.
5. The Disabilities of the Arm, Shoulder and Hand (DASH) outcome measure is a 30 question survey used to quantify the symptoms and function of any person with musculoskeletal disorders of the upper limb. It is used to determine the impact that a particular disorder has on an individual's life. [25, 26] The QuickDASH is a shortened version of the DASH that has been validated to be as significant as the full questionnaire. [27] While the QuickDash scores of RFFF subjects have not been reported, previous DASH scores have been reported to be 6.93 ± 5.54 in RFFF subjects compared to 2.95 ± 4.42 in non-RFFF subjects. [28]
6. Differences in range of motion at the hand, previously reported to be 22-27 degrees difference [8]
7. Differences in grip and pinch strength in the donor site hand, previously reported to be about a 7kg difference in pinch strength and a 0.75kg difference in grip strength. [29]
8. Wound contracture and Skin Pliability. Normal results are reported below.

Statistical Analysis:

We plan to enroll 50 subjects in each group. All hypothesis testing will two sided and performed at the 0.05 significance level. All analysis will be performed in SAS Version 9.4 (Cary, NC). No interim monitoring is planned for this study.

The analysis and estimated power for each endpoint is described below.

1. Rate of tendon exposure
 - a. We expect about a 25% rate of tendon exposure in the group that does not use Integra, while in the Integra group we hope to have a rate of tendon exposure of below 5%. We will test this hypothesis using a chi-squared test of equal proportions. We will have 81% power to detect this difference with 50 subjects in each group.

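### Item 3b's pain-severity powers (over 99% t-test, 99% Wilcoxon) do not fit the roughly 10 versus 5 subjects expected to have pain; about 56-62% and 29-35% do

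*Combined protocol and SAP*

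**What the plan says.** All of this is in section 13.0 of the combined protocol and SAP. Under Statistical Analysis: "We plan to enroll 50 subjects in each group". Tests are two-sided at 0.05.

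Item 3a gives the expected presence of pain. For the STSG group, "we expect about 20% of the subjects to still have pain at the radial forearm site"; for the Integra group, "we expect about 10% of the subjects to have pain at the radial forearm site". It then states: "We will have 29% power to detect a significant difference in pain at the radial forearm site".

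Item 3b turns to severity on a 1-10 scale and limits the comparison to a subset. It opens "Of the subjects that have pain we expect those who have had" Integra to average about 3, against 7 for those without it. On the test: "we will test if these means are equal using a t-test if data appear normal and a Wilcoxon Rank sum test if not". Two powers follow. For the t-test: "Assuming the two groups share a common standard deviation of 3, we will have over 99% power to detect this difference using a t-test". For non-normal data, the plan assumes that the probability that an Integra observation "has lower severity of pain is 0.75, we will have 99% power to detect this difference". Item 3b gives no sample size for either figure.

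**The concern.** The severity test uses only subjects with pain, and item 3a expects few of them, yet item 3b claims near-certain power. The stated figures look as if they were computed with all 50 subjects per group.

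The consequence lies in how a null result is read. Someone who takes item 3b at its word would see a non-significant severity comparison as strong evidence against a 4-point difference, because the stated risk of missing it is about 1% or less. If the real risk is many times larger, that inference fails. In addition, having pain is a post-randomisation outcome that the plan expects treatment to halve. The two subsets may therefore differ in ways that randomisation does not balance.

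**Working it through.** **Inputs (all from section 13.0).** 50 per group; two-sided 0.05; pain rates 20% and 10% (item 3a); means 7 and 3, common SD 3, or P = 0.75 (item 3b).

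**Check of item 3a.** Chi-squared test, 20% versus 10%, 50 per group, mean rate 0.15:

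z = [0.10 − 1.96·√(2·0.15·0.85/50)] / √[(0.2·0.8 + 0.1·0.9)/50] = (0.10 − 0.140)/0.0707 = −0.565, so power = 28.6%. The stated 29% reproduces, which confirms that item 3a works from 50 per group.

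**Expected subset.** 50 × 0.20 = 10 STSG and 50 × 0.10 = 5 Integra subjects with pain, before any loss to follow-up.

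**Formulas.**
- Pooled t-test: noncentral t with n1 + n2 − 2 degrees of freedom and noncentrality 4 / [3·√(1/n1 + 1/n2)].
- Wilcoxon (Noether): power = Φ(√(12·c·(1−c)·N)·|P − 0.5| − 1.96), where N = n1 + n2 and c = n1/N.

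**Reproducing the stated powers at 50 versus 50.**
- t-test: noncentrality 4/(3·0.2) = 6.67, power above 99.99%, consistent with over 99%.
- Wilcoxon, P = 0.75: √300 × 0.25 − 1.96 = 2.37, power 99.1%, matching 99%.

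**At 10 versus 5.**
- Pooled t-test: noncentrality 4/(3·√0.3) = 2.43, 13 degrees of freedom, critical value 2.16, power 61.5%. Averaged over binomial counts with pain (an empty group counted as zero power): 57.0%.
- Welch t-test, 200,000 simulated trials: 56.5%.
- Wilcoxon, P = 0.75: √40 × 0.25 − 1.96 = −0.379, power 35.2%. Exact test (reject if U ≤ 8 or U ≥ 42, actual size 0.040), simulated under a normal shift: 30.6%, or 29.1% averaged over binomial counts.

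**The two powers rest on different effects.** Under normality, 7 versus 3 with SD 3 implies P = Φ(4/(3√2)) = 0.827, not 0.75. At P = 0.827 and 10 versus 5, Wilcoxon power is 54% by Noether and by the exact test. Averaged over counts it is about 50-51%.

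**Sensitivity to the counts (STSG versus Integra subjects with pain).**

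| Counts | t-test, pooled | t-test, Welch | Wilcoxon P = 0.75, Noether | Wilcoxon P = 0.75, exact |
|---|---|---|---|---|
| 8 v 4 | 50.3% | 44.6% | 29.3% | 27.1% |
| 10 v 5 | 61.5% | 56.5% | 35.2% | 30.6% |
| 12 v 6 | 70.7% | 66.5% | 41.0% | 37.9% |
| 20 v 10 (both pain rates doubled) | 91.3% | not run | 60.9% | not run |

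**Numbers needed for the stated powers, with equal groups.** The t-test reaches 99% at 22 per group with pain (99.1%; 21 per group gives 98.8%). The Wilcoxon test at P = 0.75 needs 49 per group by Noether; in simulation, 44 per group gives 99.1%. These are minimum numbers with pain, not numbers enrolled.

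**The case against.** The arithmetic is not in dispute; the case on the other side is about weight and precision.

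- **Low stakes.** Pain severity is not in the numbered endpoint list, the sample size does not depend on it, and items 2b, 2c and 3a already admit low power for neighbouring outcomes. This stands and limits the weight. It does not make a stated power correct when the plan's own inputs contradict it.
- **Perhaps all 50 per group are analysed.** This conflicts with item 3b, which gives 7 and 3 as means among subjects with pain. It does not rescue the figures either. With pain-free subjects scored 0 or 1 and severity simulated on a bounded scale, power is about 66-70% by t-test and 34-68% by Wilcoxon.
- **The 56% end is Welch, whereas the plan assumes a common SD.** True, but the pooled test averaged over the random counts gives 57%, so the range barely moves.
- **A normal shift does not fit a 1-10 scale.** Correct: mean 3 with SD 3 puts 25% of scores below 1, and mean 7 with SD 3 puts 16% above 10. Beta distributions on 1-10 with the same means and SDs give about 59% pooled and 52% Welch. The replacement values are therefore approximate.
- **No visit is named, and pain may be commoner earlier.** Pain is surveyed at 3, 6 and 12 months (section 5.0). The documents give no higher rate. If both rates were doubled, power would be 91% by t-test and 61% by Wilcoxon, still short of 99%.
- **P = 0.75 may be a deliberate, more conservative choice for non-normal data.** That is permissible. The point is only that the two powers do not describe the same effect, and a reader should be told so.

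**Conclusion.** The concern holds. On the plan's own pain rates, power for the severity comparison is about 56-62% by t-test (difference 4, SD 3) and about 29-35% by Wilcoxon at P = 0.75, against stated values of over 99% and 99%. The risk of missing the expected difference is about 38-44% and 65-71% respectively; at P = 0.83 the Wilcoxon risk is about 46-50%.

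These figures assume that item 3a's rates apply at the visit analysed, that all 50 per group are assessed, and that severity follows a normal shift. Loss to follow-up would lower power further, a bounded scale shifts the t-test values by a few points, and none of the alternatives examined reaches the stated powers. That the full sample was used is an inference from the match at 50 versus 50, since item 3b gives no n. The text should be corrected, but nothing in the design depends on it.

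**What to change.** In item 3b:

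1. Replace the two stated powers with approximate values: about 56-62% for the t-test (difference 4, SD 3) and about 29-35% for the Wilcoxon test at P = 0.75.
2. State the expected numbers with pain, about 10 STSG and 5 Integra, and that they follow from item 3a with 50 per group.
3. State the effect assumed for each test, noting that 7 versus 3 with SD 3 corresponds under normality to P of about 0.83, where Wilcoxon power is about 50-54%.
4. Add one sentence saying that the comparison is underpowered and is made among subjects selected on a post-randomisation outcome, so it should be read cautiously.

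The cost is a less favourable stated power in one sub-item. The planned test, the data collected and the sample size do not change.

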2.1 Inclusion Criteria

- 2.1.1 All subjects who receive a radial forearm free flaps in the included time period, including subjects with head and neck cancer, traumatic defects, chronic wounds, or any other problems that require a radical forearm free flap for reconstruction.
- 2.1.2 Have had a distal, anterograde fasciocutaneous flap
- 2.1.3 Age \geq 18 years
- 2.1.4 All smokers and tobacco users will be included in this study.

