Scheduled post-operative assessments following the initial assessment will include a 3 month, 6 month, and one year follow up appointment. Evaluation at the 3-month and 6-month follow-up appointment, will include photos of the surgical site, evaluation of the skin graft and any areas of necrosis or tendon exposure, survey of presence of pain and paresthesia, and the QuickDASH survey. During the 1 year follow-up, in addition the assessments described above, the Vancouver Scale Assessment will be performed by a Co-Investigator who is blinded. Areas of tendon exposure will be treated with xeroform dressing changes.

During surgery and at the scheduled follow up all subjects will have standardized photographs taken utilizing a custom backdrop and a centimeter scale. These pictures will be used to assess wound size and dimension at each encounter, including the original surgery. This will allow us to measure the rate of wound healing, contracture, and rate of skin graft necrosis. The pictures will be analyzed with the SigmaScan planimetry program. This protocol has been previously validated and published.[15]

Subjects will be evaluated by the occupational therapy team prior to their surgery in the pre-operative holding area and during their admission to the hospital. They will be assessed using standard measurement from a goniometer and dynamometer and also given instructions for wrist range of motion exercises. During follow up, subjects will be referred to occupational and physical therapy at the discretion of the attending physician.

Subjects removed from study for unacceptable adverse events will be followed until resolution or stabilization of the adverse event.

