 - a. The Vancouver Scar Scale encompasses 4 separate outcomes to be objectively assessed. Each has been separately reported in the literature for each group in different papers as previously mentioned. We will compare the final score as well as scores within each outcome.
 - i. Vascularity (0-3): STSG group will likely average a 1, while Integra group will likely average around 0
 - ii. Pigmentation (0-2): STSG group will likely average a 1 while Integra group will likely average a 2
 - iii. Height (0-3): STSG group will be an average of about 1, while the Integra group will likely average a 0
 - iv. Pliability(1-5): We expect the STSG group to average about a 2, while the Integra group will average about a 1
 - v. Based on these scores, we would expect the STSG group to have a score of 5 while the Integra group will have an average score of about 3

We will compare these measures between the two groups using t-tests or Wilcoxon rank sum tests as appropriate. Assuming a standard deviation within each group of one and that data appears normal, we will have over 99% power to detect a difference of one and two scoring units for these tests.

5. Functional outcome as measured by pre and post-operative assessment on the QuickDASH (Disabilities of the Arm, Shoulder, and Hand) scale

The Use of Integra© in Coverage of Radial Forearm Free Flap Donor Site Defect

Comprehensive Cancer Center of Wake Forest University (CCCFWU)

CCCFWU # 99915A

- a. The survey asks the subject to rate the ease of 11 daily activities from 1-5, 1 being no difficulty, and 5 being unable to perform.
 - i. The scores are then averaged (Giving a score between 1 and 5), and one is subtracted from the average. This number is then multiplied by 25
 1. As the lowest possible rating on each activity is 1, this accomplishes bringing the lowest possible score to 0.
 2. As the highest possible rating on each activity is 5, this bring the highest possible score to be 100
 - ii. We will expect similar values as previously cited in the literature. About 70 for the subjects receiving a STSG, and values closer to 30 for the Integra group
 - iii. We will compare these two groups using t tests or Wilcoxon Rank Sum tests as appropriate. Assuming a standard deviation of 10 and that the data appears normal, we will have over 99% power to detect this difference using a two sample t test.
6. Functional outcome as measured by hand strength and Range of Motion

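### The QuickDASH outcome is defined as pre- and post-operative, but the schedule contains no pre-operative QuickDASH and the analysis has no baseline term

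*Combined protocol and SAP*

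**What the plan says.** Section 13.0, statistical analysis item 5, gives the endpoint as "Functional outcome as measured by pre and post-operative assessment on the QuickDASH". Item 5a.ii expects scores of about 70 with a split-thickness skin graft (STSG) alone and about 30 with Integra. Item 5a.iii compares the groups by two-sample t-test or Wilcoxon rank sum test and, with an SD of 10, states power over 99%. Neither sub-item mentions a change score or a baseline covariate.

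Section 5.0 holds the only schedule: "Scheduled post-operative assessments following the initial assessment will include a 3 month, 6 month, and one year follow up appointment". The content of the 3- and 6-month visits includes "survey of presence of pain and paresthesia, and the QuickDASH survey". The 1-year visit repeats these: "in addition the assessments described above, the Vancouver Scale Assessment will be performed by a Co-Investigator who is blinded".

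Before surgery, Section 5.0 says "Subjects will be evaluated by the occupational therapy team prior to their surgery in the pre-operative holding area", and gives the content as "They will be assessed using standard measurement from a goniometer and dynamometer and also given instructions for wrist range of motion exercises". No questionnaire is listed there.

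Eligibility in Section 2.1 is broad, "including subjects with head and neck cancer, traumatic defects, chronic wounds, or any other problems", and Section 2.2 does not exclude existing upper-limb disability.

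**The concern.** The two sections disagree. Section 13.0 needs a pre-operative QuickDASH, and Section 5.0 never asks anyone to collect one. Staff working from Section 5.0 would follow it correctly and still leave the defined measure without its first half. This cannot be repaired later, because a baseline not taken before surgery is gone.

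Function is part of the primary objective (Section 1.1), and the QuickDASH is the plan's patient-reported measure of it. As Section 13.0 describes it, the instrument concerns the upper limb as a whole, not the donor site alone. Without a baseline, a subject's score at follow-up cannot be divided into what was there before and what the harvest caused. Nor can the trial show whether the arms began alike, or use the baseline to sharpen the comparison.

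**Working it through.** **1. Which measures have a baseline?**

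| Measure | Before surgery (Section 5.0) | After surgery | How Section 13.0 frames it |
|---|---|---|---|
| Range of motion | goniometer | Section 13.0 item 6 | pre/post difference |
| Hand strength | dynamometer | 3, 6, 12 months (item 6b) | pre/post difference |
| QuickDASH | none listed | 3, 6, 12 months | titled pre/post; expected values given as scores |
| Pain and paresthesia | none listed | 3, 6, 12 months | presence and severity; no pre/post definition |

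Only the QuickDASH is defined as pre/post without a pre-operative collection point. For pain and paresthesia the baseline is unscheduled, but nothing in the plan calls for one.

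**2. The plan's own power figure.** Inputs from Section 13.0: 50 per group, two-sided 0.05, means 70 and 30, SD 10.
- Standard error of the difference = 10 × sqrt(2/50) = 2.0
- Difference / standard error = 40 / 2.0 = 20
- Power is above 99.9%, which agrees with the stated figure of over 99%. The calculation uses post-operative scores only.

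**3. Chance imbalance at baseline.** This assumes that the follow-up SD also applies before surgery.
- SD 10: 1.96 × 10 × sqrt(2/50) = ±3.9 points
- SD 4.42 (cited for non-RFFF subjects): 1.96 × 4.42 × 0.2 = ±1.7 points

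Only about r times the baseline imbalance carries into the follow-up contrast, where r is the correlation between baseline and follow-up. The documents give no r, so 0.3, 0.5 and 0.7 are assumed. At SD 10 the carry-over is 0.3 × 3.92 = ±1.2, 0.5 × 3.92 = ±2.0 and 0.7 × 3.92 = ±2.7 points.

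**4. Gain from adjustment.** The residual SD after ANCOVA is SD × sqrt(1 − r²). A change score has SD × sqrt(2(1 − r)). For the power columns the difference is 6.93 − 2.95 = 3.98, the only DASH contrast the plan cites, with SD 10 and 50 per arm (noncentral t, 98 df). Post-operative scores alone give 50% power.

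| Assumed r | Variance removed (r²) | ANCOVA SD | Change-score SD | Power, ANCOVA | Power, change score |
|---|---|---|---|---|---|
| 0.3 | 9% | 9.5 | 11.8 | 54% | 38% |
| 0.5 | 25% | 8.7 | 10.0 | 62% | 50% |
| 0.7 | 49% | 7.1 | 7.7 | 79% | 72% |

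A raw change score does worse than ignoring the baseline when r is below 0.5. ANCOVA does not.

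**5. Sensitivity to the SD.** The 3.98 contrast comes from data with SDs of 5.54 and 4.42, pooled sqrt((5.54² + 4.42²)/2) = 5.01. At that SD the standard error is 5.01 × 0.2 = 1.0, and power for 3.98 points is already about 98% without a baseline (normal approximation: 3.98/1.0 − 1.96 = about 2.0). The precision gain is therefore material when the difference is small relative to the SD, and not otherwise.

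**The case against.** **Randomization protects the comparison.** This stands. Pre-existing disability is balanced in expectation, and the t-test's standard error already allows for chance imbalance. A reader might infer from the missing baseline that the treatment comparison is confounded by prior limb disability. The documents do not support that.

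**The planned effect is very large.** This also stands on the plan's own terms. Against 40 points, ±3.9 is about 10%, and power is above 99% with or without a baseline. But the expectation of 70 versus 30 is said to follow the literature, while the only DASH scores cited are 6.93 and 2.95, so the design should not lean on it.

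**The ±3.9 could be overread.** A reader might note that it nearly equals the cited 3.98-point contrast and conclude that imbalance could account for a whole treatment effect. It could not be read that way: ±3.9 is an imbalance in baseline means, of which only a fraction r carries over. It rests on an SD about twice that of the cited data. The 3.98 compares RFFF with non-RFFF subjects, whereas both arms here have the flap.

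**A baseline may be intended.** Item 5 does call for one, and Section 5.0 refers to an initial assessment. That assessment is not defined and no questionnaire is assigned to it, so it does not fill the gap. Item 5a.iii could be meant to compare changes, but the expected values are scores and no change is mentioned.

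**Prior disability is not shown.** Fair. The eligibility criteria list reasons for reconstruction and do not show that the donor arm is impaired. They make prior disability possible, not established.

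**Pain and paresthesia.** It is tempting to include these in the contradiction. No section defines them as pre/post endpoints, and item 3 places pain at the forearm site. A baseline survey would be useful but optional.

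**Conclusion.** The point holds for the QuickDASH. Sections 5.0 and 13.0 cannot both be followed as written: the outcome is titled pre- and post-operative, and the schedule supplies only the post-operative part. The losses are within-subject change, attribution to the donor site, a check on chance imbalance, and precision. Validity of the randomized comparison is not among them.

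The precision at stake is 9% to 49% of residual variance, for assumed correlations of 0.3 to 0.7. It changes nothing at the planned 40-point difference. For a difference near 4 points with SD 10, it moves power from 50% to between 54% and 79%; with an SD near 5, power is high already. The 4-point figure illustrates scale only and does not predict the Integra effect.

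This should be corrected before further subjects are enrolled, because the data cannot be collected afterwards. It does not undermine the trial.

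**What to change.** - **Section 5.0:** add the QuickDASH to the existing pre-operative occupational therapy evaluation, completed before surgery, and state what the initial assessment consists of.
- **Section 13.0, item 5:** compare the arms on the follow-up QuickDASH by ANCOVA, with the pre-operative score as covariate, in place of the unadjusted t-test. This is preferable to a raw change score, which loses precision when the correlation is below 0.5.
- **Optional:** give the pain and paresthesia survey at the same contact.

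The cost is one 11-item questionnaire at a contact that already takes place, a few minutes of pre-operative time, one more REDCap time point and a wording amendment. No visits or subjects are added. If the sponsor does not want a baseline score, the minimum is to reword item 5 as a post-operative outcome. That removes the contradiction but recovers none of the lost information.
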